3.2. Corticosteroid therapy

3.2.1. Oral prednisone

Prednisone vs. alternative oral corticosteroid

Unless contraindicated, oral prednisone should be used. An equivalent dose of an alternative oral corticosteroid may be used only if a specific contraindication to oral prednisone is present. All references to oral corticosteroid and specific dosing schedules presented in this Manual of Procedures are given for oral prednisone.

Initial dose

All patients enrolled in the study will be initially taking concomitant oral corticosteroids at 1 mg/kg or 60 mg daily, whichever is less. Treatment success is dependent upon successfully tapering concomitant prednisone to 7.5 mg/day. Initial corticosteroid dose will be continued for 2 to 4 weeks at which point prednisone will be gradually tapered.¹ Prednisone will be tapered to and held at 7.5 mg/day for the first 6 months of the study. Further reduction of corticosteroids will be allowed in Phase I after six months. If patients switch treatments and enter Phase II due to a failure of efficacy in Phase I, they will follow the same protocol as the initial Phase I corticosteroid

treatment and begin at 1 mg/kg or 60 mg, whichever is less. In patients failing for efficacy, investigators may start at a lower prednisone dose if they feel it is medically indicated. However, following the corticosteroid tapering guidelines is strongly encouraged. If patients switch treatments and enter Phase II due to a failure of intolerability in Phase I, then it is at the study doctor's discretion at what dose of corticosteroid to start the patient.

Tapering schedule

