< 7.5 & ≥ 5	2 – 4	1 - 2.5
< 5 & ≥ 2.5	2 - 4	1.5 - 2.5
< 2.5 & ≥ 1	2 – 4	1
0		

NOTE: When beginning Phase I (6-12 months), hold patient at 7.5 mg/day, for at least one week.

Directions for Rescue Taper

Reactivations can be mild or severe. Mild reactivations are considered an increase in inflammation up to the 1+ level in anterior chamber cell or vitreous haze. Severe reactivations are considered an increase in inflammation up to the 2+ level or higher in anterior chamber cell or vitreous haze. Retinal/choroidal lesions may be considered mild or severe at the discretion of the study physician.

If uveitis reactivates:

- Increase oral prednisone up to a dose of 1 mg/kg for severe reactivations, or for mild reactivations, up to double the dose at which the flare occurred, until uveitis is controlled. Then re-taper according to the guidelines.

Uveitis is considered non-responsive if inflammation does not increase but does not further improve after the first 4 weeks of treatment on 1mg/kg oral prednisone.

If uveitis is non-responsive:

- Hold the current dose of prednisone for an additional week. If still no improvement, treatment failure due to futility may be declared, and patients may proceed to Phase II. Alternatively, other therapies may be added, but these should be noted as a protocol deviation.
- If treatment failure is declared due to futility in Phase I, before the primary endpoint of 6 months, patients may switch to Phase II. Patients who refuse to switch to Phase II should be encouraged to return for a 6-month visit. Patients who switch to Phase II will already be followed.
- If treatment failure is declared due to futility in Phase II, before the primary endpoint of 6 months, patients will be treated according to best medical judgment. If treatment failure is declared prior to 6 months, Phase I and Phase II, every attempt must be made to bring patients back for their 6 month assessment.

After suppression of uveitis is once again achieved (either in the case of reactivation or non-response) follow the taper guidelines for Phase I. Patients who have failed the treatment to which they are randomized will then switch treatments, begin Phase II, and follow the same taper guidelines as Phase I (0-6 months). If patients flare during Phase II, they can follow directions for the rescue taper listed above. Patients who fail the second treatment at the 6 month endpoint will be treated as per the investigators discretion.

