categories: anterior/intermediate or intermediate only, and posterior/panuveitis). Anatomical location by history is considered the prespecified analysis; anatomical location at enrollment will supplement this finding.

We propose to proceed as follows. We propose to begin with Equation (1), adding terms $\beta_3 X_i^3 + \beta_{13} X_i^1 X_i^3$ for anatomic location and for treatment-location interaction. We wish to test the hypothesis that $\beta_{13} = 0$, i.e. that there is a difference in treatment efficacy between the anatomic locations, controlling for country. Alternative models will be fit in which the country, site, and treatment x country terms are omitted.

We will also report relative risks in each substratum, using relative risk regression.

Additional analyses will add gender and age to the predictors. The entire analysis will be repeated for each gender, and separately for each country (US and India) and anatomic location.

Planned Secondary Analyses.

Each of the following secondary analyses is designed to test the hypothesis that treatment assignment affects a given outcome, after controlling for selected covariates. All analyses will be repeated without controlling for covariates (i.e., using treatment assignment as the only predictor). In all cases, appropriate regression diagnostics and/or goodness of fit tests will be performed (further details are given below). In addition, we will compute jackknife influence statistics in each analysis, to determine whether or not any single observation (eyes or patients, as appropriate) have an undue effect on the final conclusion. All models with site effects will be repeated omitting this effect, and again repeated including a treatment-site effect, and with country and/or treatment by country interactions (i.e., pooling within countries when appropriate). When reporting findings, care will be taken to distinguish the single prespecified test from supplemental tests (whether prespecified or unprespecified); exploratory analyses will always be labeled as such. All alpha levels are to be two-sided.

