3. *Country and site within country.* We denote the country by X_i^2 , which will be 0 for US locations and 1 for Indian locations; X_n^4 is 1 only for patients in the second Indian site and 0 otherwise, while X_{iz}^4 is 1 only for patients in the second US site and 0 otherwise. As mentioned under the Primary analysis, we propose to fit models with country only, drug by country interaction, and with a drug by country interaction, including site within country as well. Analysis will be conducted within each site, then pooling the sites within country together. Further details regarding pooling across centers are provided above under the main prespecified analysis.

4. *Best spectacle-corrected visual acuity (BSCVA).* The primary outcome variable for this secondary outcome will be the change in best spectacle-corrected visual acuity from baseline to final (as defined in the FAST MOP, i.e. for those who successfully control inflammation as defined in the MOP, or at the time of failure for those who fail; MOP, Section 2.6). Visual acuity change scores are available for both eyes for each patient.

The primary analysis will use a linear mixed-effects regression, where the outcome variable is the change in BSCVA in each eye, using treatment assignment as a statistical predictor (regressor, independent variable); a random effect will be used at the individual level, because of the possibility that changes in the two eyes from a given patient are correlated. In a supplementary analysis, we will include as predictors (independent variables) anatomic location of uveitis, interaction between anatomic location and treatment assignment, and the study site, together with a random effects for patient. We will fit these models using maximum likelihood (R procedure `lmer`) and use likelihood-ratio tests to test the hypothesis that treatment assignment affects BSCVA change. Only eyes that are eligible and meet inflammation criteria at baseline will be included in this analysis. If at a given visit, vision cannot be assessed, we will carry the last observation forward. Additional sensitivity analyses for missing data will be used (including mixed effects models controlling for time, including all data from an individual).

Also, if there is no eye at Month 6 to assess, the patient will be given a logMAR value of 2.0.

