Because of the possibility that the outcome variable (BSCVA change score) will exhibit non-normality, we will repeat the analyses using transformations of the outcome data (including power and log transformations, or more general monotone transformations).

Additional analyses will be performed using age, gender, ethnicity, and the steroid dose at each month as predictors.

An additional supplemental analysis will be conducted using final BSCVA (instead of the change score) as the outcome, and including baseline BSCVA in each eye as a predictor, using methods otherwise identical to those above.

5. *Quality of life.* We will also use a linear mixed model to assess health-related quality of life, measured by the SF-36 questionnaire (PCS and MCS scores) and vision related quality of life NEI-VFQ-25 and IND-VFQ at 6 months or at the time of failure, as described in the Manual

of Operations. Predictors will be baseline quality of life, age, gender, ethnicity, study site (as a random effect), and treatment assignment, and we will test the hypothesis that the regression coefficient corresponding to treatment assignment equals zero using the Wald t-test. Similar assessments will be performed for vision-related quality of life questionnaires.

6. *Reason for discontinuation.* Individuals who discontinue study medication may do so due to inability to tolerate side effects, due to lack of efficacy, or for safety reasons. The outcome variable is whether the person discontinued due to intolerance, discontinued due to lack of efficacy, discontinued due to safety, or did not discontinue the medication. Because study site may be an important factor, we will use polytomous regression to model the discontinuation result as a function of treatment assignment (using a fixed effect for study site).⁷ If evidence is found that treatment assignment influences discontinuation result, further analyses may be conducted to determine whether or not treatment assignment is associated with discontinuation due to intolerance, lack of efficacy, or to safety, or some combination of these. We propose to classify all individuals in a two by four table according to treatment assignment and discontinuation (not discontinued, discontinued due to intolerance, discontinued due to lack of efficacy, discontinued due to safety) and conduct the Fisher's exact test (in its $r \times c$ form). The use of an overall test prior to further analysis is designed to protect the overall error rate.

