Multiple imputation will be conducted as follows. The following information will be used as regression covariates: (i) age, (ii) gender, (iii) inflammation assessments at all prior time points (anterior cells, vitreous haze, and retinal/choroidal lesions), (iv) steroid dose, (v) anatomic location (by patient, classified as anterior/intermediate or posterior/panuveitis), (vi) anatomic location by history, (vii) maximum steroid dose within the 90 days prior to enrollment, (viii) steroid dose at enrollment prior to randomization or study-related intervention, (ix) country, and (x) site within country. Any additional covariates must be prespecified. A regression model for the missing outcome information will be derived; specifically, a cross-validated procedure to yield the best prediction based on complete subjects will be derived, and ten multiple imputations will be derived from it. The formula in Little and Rubin²⁵ will be used to derive the overall test statistic. All replications will be recorded and reported.

An alternative method (which we propose to use for sensitivity analysis) is hot deck multiple imputation (with ten replications).²⁵ Note that treatment assignment would never be missing. For definiteness, we choose the recursive random partitioning hot deck method used in the R package `rrp` with the default settings (command `rrp.impute`).

The possibility of data-driven modeling may render multiple imputation of an outcome variable undesirable to many reviewers as a primary outcome. An alternative method is to model the treatment success of person i at visit j , Y_{ij} , using generalized linear mixed models, with covariates being site, country, treatment assignment, country-assignment interaction, visit (1:6), and visit-drug interaction (method 2 above). Note that additional statistical modeling will be reported, in which we (a) omit visit-drug interaction, and/or country assignment interaction, (b) add visit-country interaction, or (c) add age or gender as covariates.

We believe carrying forward last observations to be particularly unhelpful in this study, because all patients are on a prescribed steroid taper. We also believe that differential loss to follow-up of well performing patients on one drug or the other could falsely make the poorer drug appear to give more favorable results, so that the complete case analysis must be interpreted with caution.

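### One additional visual acuity analysis adjusts for monthly steroid dose, which is partly a result of the study drug, so its treatment coefficient does not estimate the drug effect

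*Combined protocol and SAP*

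**What the plan says.** SAP 3.2.2 (Planned Secondary Analyses) introduces the secondary analyses as tests of whether treatment assignment affects each outcome after adjustment for chosen covariates. Item 4, on BSCVA, has three layers:

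- **Main model.** A linear mixed model for change in each eye, with a patient random effect, "using treatment assignment as a statistical predictor (regressor, independent variable").
- **Supplementary model.** "In a supplementary analysis, we will include as predictors (independent variables) anatomic location of uveitis, interaction between anatomic location and treatment assignment", plus study site.
- **Further models.** "Additional analyses will be performed using age, gender, ethnicity, and the steroid dose at each month as predictors".

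Only the third layer contains steroid dose. Two general statements in the same section also apply: "All analyses will be repeated without controlling for covariates (i.e., using treatment assignment as the only predictor"), and "care will be taken to distinguish the single prespecified test from supplemental tests".

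Protocol 3.2.1 sets out how dose is determined. Under Initial dose: "Treatment success is dependent upon successfully tapering concomitant prednisone to 7.5 mg/day". Under Directions for Rescue Taper, if uveitis reactivates: "Increase oral prednisone up to a dose of 1 mg/kg for severe reactivations, or for mild reactivations, up to double the dose".

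SAP 3.5 lists two doses fixed before randomisation among its imputation covariates: "vii) maximum steroid dose within the 90 days prior to enrollment, (viii) steroid dose at enrollment prior to randomization or study-related intervention".

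**The concern.** Monthly dose is measured after randomisation and responds to the drug being tested. If one drug controls inflammation better, its patients flare less and stay nearer the scheduled taper. Holding dose fixed then does two things. It removes the part of the drug effect on acuity that goes with better control of inflammation. It also makes the arms non-comparable within a dose level, because a patient kept on a low dose by the better drug may have worse underlying disease than a patient on the same dose with the weaker drug.

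At stake is a prespecified acuity estimate that could differ from the main one for artefactual reasons, possibly against the drug that spares steroids. The SAP attaches no estimand, mediation aim or caution to this model. The covariates around it are of a different kind: the additional regression variables in SAP 3.2.1 are baseline or fixed, and the quality-of-life model in item 5 uses no dose.

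The covariate is also incompletely defined. SAP 3.2.1 takes acuity at failure or at six months, so patients who fail early have no first-drug dose for later months. The SAP does not say how those months are filled.

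**Working it through.** **Step 1: the plan's own figure.** SAP 3.4.2 item 3 gives an SD of change of 6.5 letters and about 80% power for 2.63 letters. SAP 3.4.1 gives 108 per arm and 10% loss, so about 97 per arm. A two-sided alpha of 0.05 is assumed, since none is stated specifically for BSCVA.

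- Normal approximation: (1.960 + 0.842) × 6.5 × √(2/97) = 2.615 letters.
- Two-sample t-test, 97 per arm: 2.628 letters detectable, and 80.1% power at 2.63. This reproduces the SAP.
- With 108 per arm it would be 2.489 letters, so 2.63 already allows for the loss.

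**Step 2: when dose reflects response.** Table 6 of the protocol has 2 to 4 weeks at the starting dose, then ten one-week steps, then a hold at 7.5 mg/day. That is 12 to 14 weeks, or 84/30.44 = 2.8 to 98/30.44 = 3.2 months. At months 4 to 6 a patient on schedule is at the hold dose, so differences mainly reflect flares, rescue tapers or departures from schedule.

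**Step 3: bias formula.** Let T be arm (1 = better steroid-sparing drug) and D be dose in within-arm SD units, with D = −aT + e. Let acuity change be Y = τT + 6.5(ρe + √(1−ρ²)u), where ρ is the within-arm correlation of dose with acuity change. Substituting e = D + aT:

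adjusted effect = τ + 6.5ρa

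SE = 6.5 × √(1−ρ²) × √(2/97) × √(1 + a²/4)

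The documents give neither a nor ρ, so both are assumptions. For scale, a = 0.507 is the probit shift between the planned success rates of 0.4 and 0.6 (0.2533 + 0.2533). A smaller shift of 0.25 is also shown.

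Example with a = 0.507, ρ = −0.4: 2.63 − 6.5 × 0.4 × 0.507 = 1.31 letters. SE = 0.88, so power is 32%.

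| a | ρ | True 2.63: estimate (power) | True 0: estimate (significant against the sparing drug) |
|---|---|---|---|
| 0.25 | −0.2 | 2.30 (71%) | −0.33 (5%) |
| 0.25 | −0.4 | 1.98 (63%) | −0.65 (11%) |
| 0.25 | −0.6 | 1.65 (60%) | −0.97 (25%) |
| 0.507 | −0.2 | 1.97 (55%) | −0.66 (10%) |
| 0.507 | −0.4 | 1.31 (32%) | −1.32 (32%) |
| 0.507 | −0.6 | 0.65 (14%) | −1.98 (73%) |
| 0.507 | 0 | 2.63 (78%) | 0 (2.5%) |
| 0.507 | +0.2 | 3.29 (94%) | +0.66 (0.4%) |

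A 2.63-letter benefit changes sign only if |ρ| × a exceeds 2.63/6.5 = 0.405.

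**Step 4: simulation checks.** With 97 per arm and 5,000 runs, a = 0.507 and ρ = −0.4 gave 1.29 letters (31% power) for a true 2.63. For a true zero it gave −1.32 letters, significant against the sparing drug in 31.7% of runs.

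A second simulation used six monthly doses driven by inflammation, with unmeasured severity costing 2 letters per SD. Dose adjustment gave −0.91 letters for a true zero and 1.78 for a true 2.63. When severity had no effect on acuity and steroid itself improved it, the unadjusted difference was 1.84 letters and the adjusted one 2.64.

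These calculations use one value per patient, as the SAP's power calculation does. The planned model is at eye level with a patient random effect.

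**The case against.** The strongest reply is that little depends on this model. The SAP calls it additional, keeps dose out of the main and supplementary models, repeats every secondary analysis with treatment alone, and undertakes to separate the prespecified test from supplemental ones. No alpha allocation or stopping rule uses it. All of this stands. A reader might infer that the trial's visual acuity result as a whole is biased by steroid adjustment. The documents do not support that.

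A second reply is that dose has other causes. The starting dose depends on body weight and known tolerability, the starting period varies by two weeks, visit windows are ±15 days, and investigators may taper faster for side effects. The study drugs also need 6 to 8 weeks for full effect. This is fair for the early months and is why the argument rests mainly on months 4 to 6.

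A third reply is that prednisone is active treatment, so adjusting for it asks a different question that is not meaningless. That is true, as the last simulation shows. It is still not the question SAP 3.2.2 sets for its secondary analyses, and the answer requires no unmeasured common cause of dose and acuity, which is hard to defend when disease severity drives both.

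It might also be inferred that Phase II doses on the other drug enter the model for patients who switch early. The SAP does not say so. What can be said is that the handling of months after failure is unspecified.

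**Conclusion.** The point holds for one additional analysis of one secondary outcome. Its treatment coefficient does not estimate the randomised drug effect, because it conditions on a variable that the drug influences.

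It is tempting to say that the adjustment always shrinks a real benefit or turns it against the better drug. The documents do not support that, since they give neither the between-arm dose difference nor the relation of dose to acuity. Where higher dose marks worse acuity, the distortion can be material: over the assumed correlations of −0.2 to −0.6, the estimate of a true 2.63 letters falls by 0.33 to 0.98 letters at a shift of 0.25 SD, and by 0.66 to 1.98 letters at 0.507 SD. At 0.507 SD, reversing the sign of a true 2.63 letters would need a correlation stronger than about −0.80 (0.405/0.507). A spurious negative result is easier to produce when the true acuity effect is near zero. If the arms do not differ in dose, or dose is unrelated to acuity within arm, there is no bias. If higher dose goes with better acuity, a benefit is overstated.

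Severity is low.

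**What to change.** In SAP 3.2.2 item 4, replace the monthly steroid dose with the two pre-randomisation doses already listed in SAP 3.5: the maximum in the 90 days before enrollment, and the dose at enrollment before any study intervention. Report monthly dose by arm descriptively, as an outcome.

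If a dose-adjusted model is kept, label it exploratory, state that it is not an estimate of the treatment effect, and say how months after failure are handled. A question about how far the effect operates through steroid dose would need its own stated method and assumptions.

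The cost is a sentence or two in the SAP. The replacement covariates are already planned for the imputation model, so no new data are needed. The main BSCVA test, the sample size and patient care do not change.
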